- 1 (Yes) = biochemical relapse: confirmed  $ALT > 2 * ULN$ .
- 0 (No) = no biochemical relapse: at least one post-treatment measurement available and not a viral relapse
- 2 (Not applicable) = no post-treatment ALT measurements available

---

- 3 (No: ongoing) = no biochemical relapse: at least one post-treatment measurement available and not a biochemical relapse but still ongoing (only for interim analysis)

Confirmed means that the criterion should be fulfilled at 2 or more consecutive time points or at the last observed time point.

Note: biochemical relapse will only be assessed for those subjects who at the actual end of treatment have  $ALT \leq ULN$ .

*Clinical viral relapse is defined as follow:*

- 1 (Yes) = if both viral and biochemical relapse
- 0 (No) = otherwise and not ongoing
- 2 (Not applicable) = no post-treatment measurements available
- 3 (No: ongoing) not both viral and biochemical relapse but still ongoing (only for interim analysis)

Note: clinical viral relapse will only be assessed for those subjects who at the actual end of treatment have  $HBV\ DNA < 20\ IU/ml$  detectable/ undetectable and  $ALT \leq ULN$ . *Seroconversion of HBsAg (all subjects) / HBeAg (positive subjects) at week 24 of the treatment and at week 48 of the treatment (only subjects with treatment extension)* is defined as a confirmed loss of HBsAg/HBeAg at week 24/48 of the treatment. Loss is defined as a baseline HBeAg /HBsAg (qualitative) with a "REPEAT REACTIVE, CONFIRMED" or "POSITIVE" result and a post-baseline assessment with a "NEGATIVE" result.

*Seroconversion of HBsAg (all subjects) /HBeAg (positive subjects) at week 24 of the treatment and at week 48 of the treatment (only subjects with treatment extension)* is defined as:

- Use the selected time point for the week 24 or 48 visit as described in 2.3.
- A confirmed loss of HBsAg/HBeAg at week 24/48-of the treatment (i.e. seroclearance)
- and an appearance of Anti-HBs/Anti-HBe.

Loss is defined as a baseline HBeAg /HBsAg (qualitative) with a "REPEAT REACTIVE, CONFIRMED" or "POSITIVE" result and a post-baseline assessment with a

---

"NEGATIVE" result. Appearance is defined as a baseline Anti-HBs/ Anti-HBe (qualitative) with a "NEGATIVE" result and a post-baseline assessment with a "POSITIVE" result. Both criteria should be fulfilled.

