### 5.2.1 Secondary Analysis

- Descriptive statistics of the actual values (original unit and log10 transformed values) and the change from baseline (log10 transformed values) over time for qualitative viral activity parameters according to the specification described in section 2.6 will be included.
- LS means (SE) of change from baseline (and 95% confidence interval) for qualitative viral activity parameters per time point and overall based on log10 transformed values will be analyzed by subject population and part using mixed effects model for repeated measures similar as described in section 5.2.1.1.. Also P-values for treatment, time, their interaction and overall will be added.
- LS means (SE) of change from baseline (and 95% confidence interval) for qualitative viral activity parameters (except for HBeAg) per time point and overall based on log10

---

transformed values will be analyzed by subject population, part and by HBeAg status using mixed effects model for repeated measures similar as described in section 5.2.1.1. Also P-values for treatment, time, their interaction and overall will be added.

- A tabulation of the proportion of subjects with virological breakthrough during 24 week treatment and during 48 week treatment (only subjects with treatment extension) will be included.
- A tabulation of the proportion of subjects with viral relapse will be provided. For the purpose of the analysis, the denominator will only include those subjects with values Yes and No.
- Descriptive statistics of the maximum decrease from baseline ( $\log_{10}$  transformed values) over time for qualitative viral activity parameters according to the specification described in section 2.6 will be included.
- A tabulation of the status change from baseline at week 24 and at week 48 (only subjects with treatment extension) will be displayed by viral activity parameter.
- A tabulation of the proportion of subjects who meet the criteria of response categories per time point defined in section 5.3.1 will be displayed by viral activity parameter.
- A tabulation of the proportion of subjects who meet the criteria of response categories per period defined in section 5.3.1 (additional information in the table) will be displayed by viral activity parameter.
- A tabulation of the qualitative result of HBeAg and HBsAg per timepoint (week 24 and week 48) will be included.
- A tabulation of the biochemical response per time point will be included.

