- All individual values will be presented in subject listings: (1) including all subjects, (2) including subjects with viral breakthrough during 24 weeks or 48 weeks treatment (only subjects with treatment extension) and (3) including subjects with viral relapse.
- Mean (+/- SE) plots of the actual ( $\log_{10}$  transformed) values for all viral activity parameters will be presented by parameter.
- Mean (+/- SE) plots of the change from baseline for all viral activity parameters will be presented by parameter.
- A plot representing all actual ( $\log_{10}$  transformed) values of all viral activity parameters for each subject will be included. One graph per subject.
- The actual ( $\log_{10}$  transformed) values over time are plotted per the viral activity parameter. Each line will represent one subject.
- The change from baseline ( $\log_{10}$  transformed values) over time are plotted per the viral activity parameter. Each line will represent one subject.

---

The proportion of subjects for the secondary categorical endpoints below will be categorized by treatment group, HBeAg status and overall (pool HBeAg status) during study treatment and follow-up and where appropriate the difference between proportions and Clopper-Pearson 95%CIs may be calculated using a chi-square test of equal proportions.

- The proportion of subjects with a viral breakthrough
- The proportion of subjects with HBsAg seroclearance
- The proportion of subjects with HBsAg seroconversion
- The proportion of subject with viral relapse
- The proportion of subjects with HBsAg reduction
- The proportion of subjects with HBeAg reduction
- The proportion of subjects with HBVDNA reduction
- The proportion of subjects with HBV RNA reduction
- The proportion of subjects with biochemical relapse
- The proportion of subjects with clinical viral relapse

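### Code 0 (No) of biochemical relapse tests for viral relapse, so some subjects get no code and others get two

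*SAP*

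**What the plan says.** SAP Section 5.3, Parameter Definitions (sub-heading numbered 5.2.1), gives biochemical relapse in the follow-up phase four codes:

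- Code 1: "1 (Yes) = biochemical relapse: confirmed" ALT above 2 × ULN.
- Code 0 (No): "no biochemical relapse: at least one post-treatment measurement available and not a viral relapse".
- Code 2: "2 (Not applicable) = no post-treatment ALT measurements available".
- Code 3, for interim analyses only: "at least one post-treatment measurement available and not a biochemical relapse but still ongoing".

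Only subjects with ALT at or below ULN at the actual end of treatment are assessed. Viral relapse is defined just before, with the same four-code scheme and the same closing condition in its own code 0. It is assessed in a different set of subjects: those with HBV DNA below 20 IU/mL at the actual end of treatment.

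The Secondary Analysis part of the same section lists "The proportion of subjects with biochemical relapse" among the secondary categorical endpoints and gives no denominator for it. The statement that "the denominator will only include those subjects with values Yes and No" stands only in the bullet on tabulating viral relapse.

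**The concern.** Yes is an ALT event and No is the absence of an HBV DNA event, so the two are not complements. The wording looks carried over from the viral relapse definition, because code 3 of the same variable names the right event.

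The discordant subjects are not a purely theoretical group. Protocol Section 2.1 has separate endpoints for virologic relapse and for clinical relapse (virologic relapse together with raised ALT). One of the re-treatment criteria in Protocol Section 6.4 is an HBV DNA threshold with no ALT condition. The plan itself therefore expects that virus may return without an ALT relapse.

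At stake is a listed secondary proportion. Classification by the code as written depends on a virological outcome, and the effect can differ between arms if viral relapse rates differ. Two programmers following the SAP could report different rates from the same data.

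**Working it through.** The documents give no figure for this endpoint, so there is none to reproduce. The check applies the codes literally and then follows the result into the proportion.

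**Step 1: codes at the final analysis.** Take a subject with ALT at or below ULN and HBV DNA below 20 IU/mL at end of treatment, with post-treatment ALT available. Code 2 does not apply, and code 3 is for interim analyses only.

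| ALT relapse | Viral relapse | Codes met as written | Intended code |
|---|---|---|---|
| No | No | 0 | 0 |
| No | Yes | none | 0 |
| Yes | No | 1 and 0 | 1 |
| Yes | Yes | 1 | 1 |

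Only the two concordant rows are coded cleanly. The empty row covers every subject without confirmed ALT above 2 × ULN, including those with ALT between 1 and 2 × ULN.

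**Step 2: subjects outside the viral relapse set.** A subject with ALT at or below ULN but HBV DNA of 20 IU/mL or more at end of treatment is assessed for biochemical relapse and not for viral relapse. Whether code 0 is met cannot be determined from the text.

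**Step 3: effect on the proportion.** Let M be assessed subjects with post-treatment ALT, Y those with ALT relapse, b those with both relapses, and v those with viral but no ALT relapse. For simplicity, viral relapse is taken as assessable in all M. The intended rate is Y/M. The SAP leaves open both the denominator and which code wins in the overlap:

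- Yes + No denominator, code 1 first: Y/(M − v), an inflation factor of M/(M − v).
- All assessed as denominator, code 1 first: Y/M, unchanged.
- Code 0 overrides code 1: b/(M − v) with Yes + No, or b/M with all assessed.

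**Step 4: illustrations.** All counts are assumed; none comes from the documents.

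First set: M = 30, Y = 4, b = 3, intended rate 4/30 = 13.3%.

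| v | Yes + No, code 1 first | All assessed, code 1 first | Yes + No, code 0 overrides |
|---|---|---|---|
| 0 | 4/30 = 13.3% | 13.3% | 3/30 = 10.0% |
| 3 | 4/27 = 14.8% | 13.3% | 3/27 = 11.1% |
| 6 | 4/24 = 16.7% | 13.3% | 3/24 = 12.5% |
| 12 | 4/18 = 22.2% | 13.3% | 3/18 = 16.7% |

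Second set: 2 with both relapses, 4 with ALT relapse only, 4 with viral relapse only, 20 with neither. The intended rate is 6/30 = 20.0%. Code 1 first with Yes + No gives 6/26 = 23.1%. Code 0 overriding gives 2/26 = 7.7% with Yes + No and 2/30 = 6.7% with all assessed.

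**Step 5: the corrected wording.** If code 0 means no biochemical relapse, each of the four rows gets exactly one code and the rate is Y/M.

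**The case against.** The strongest reply is that the intent is plain. Code 0 is labelled as no biochemical relapse, code 2 refers to ALT, code 3 names the right event, and the population is restricted on ALT. A programmer would probably read it as intended or raise a query. That stands as a reason to call this a drafting error and not a chosen method. It does not remove the need to correct it: the SAP is the derivation specification, and a silent correction would be an undocumented departure from it.

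A second reply is that little depends on it. The protocol's relapse endpoints are virologic and clinical relapse; biochemical relapse alone appears only in the SAP. Clinical viral relapse is No for everyone who is not Yes and not ongoing, so it does not have this gap. The study is exploratory with no formal hypothesis testing. The number of affected subjects is not known and could be zero. All of this stands and limits the weight of the point.

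A reader might infer that the biochemical relapse rate is overstated. The documents do not support that as a general statement. The Yes/No denominator is written only for viral relapse, and with all assessed subjects as denominator and code 1 first there is no inflation. The overlap between codes 1 and 0 can push the rate down. At an interim analysis, code 3 does cover an ongoing subject with viral but no ALT relapse. Nor do the documents say how common that pattern is.

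**Conclusion.** The definition is wrong as written. At the final analysis the codes are neither exhaustive nor mutually exclusive, and for one group of assessed subjects code 0 cannot be evaluated. This follows from the text alone.

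The size and direction of any error in the proportion are conditional. Inflation by M/(M − v) requires v above zero, a Yes + No denominator and code 1 taking precedence. There is no error with all assessed subjects as denominator and code 1 first. Understatement is possible, though not certain, if code 0 overrides code 1. The percentages above show the mechanism only. The point is a definite specification error in a secondary, SAP-only endpoint.

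**What to change.** Reword code 0 of biochemical relapse so that it requires at least one post-treatment ALT measurement and the absence of a biochemical relapse. Naming ALT also settles which measurement is meant and removes the dependence on HBV DNA at end of treatment. In Secondary Analysis, state that the denominator for the biochemical relapse proportion is Yes + No.

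The cost is one line in the definition, one sentence on the denominator and the matching change in the derivation program. Data collection and study conduct are unaffected. The change should be documented before the final analysis.

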
 
To evaluate efficacy in terms of HBsAg (in all subjects) or HBeAg (in HBeAg-positive subjects only) seroclearance and/or seroconversion.
 
	
 
Proportion of subjects with HBsAg or HBeAg seroclearance (defined as HBsAg or HBeAg negativity, respectively, based on the assay used) during study treatment and follow-up.
 
Proportion of subjects with HBsAg or HBeAg seroconversion (defined as HBsAg or HBeAg negativity and anti-HBs or anti-HBe antibody positivity, respectively) during study treatment and follow-up.
 

 
To evaluate the frequency of subjects with biochemical response.
 
	
 
Proportion of subjects with ALT improvement and normalization during study treatment and follow-up.
 

 
To evaluate the frequency of HBV virological breakthrough.
 
	
 
Proportion of subjects with virological breakthrough during study treatment defined as confirmed on-treatment HBV DNA increase by <math>>1 \log_{10}</math> from nadir level or confirmed on-treatment HBV DNA level <math>>200</math> IU/mL in subjects who had HBV DNA level below the lower limit of quantification (LLOQ) of the HBV DNA assay.
 

 
To evaluate the potential effect of JNJ-56136379 on the pharmacokinetics of NA when coadministered.
 
	
 
Pharmacokinetics of NA when administered as monotherapy or when coadministered with JNJ-56136379.
 

Objectives	Endpoints

 
To evaluate the pharmacokinetics of JNJ-56136379 when administered as monotherapy.
 
To evaluate the potential effect of NA on the pharmacokinetics of JNJ-56136379 when coadministered.
 
To assess changes in the HBV genome sequence.
 
	
 
Pharmacokinetics of JNJ-56136379 when administered as monotherapy or when coadministered with an NA.
 
Emergence of treatment-associated mutations during study treatment and follow-up.
 

Exploratory	

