### **11.3.3. Other Analyses**

Mean changes and maximum mean decrease from baseline in HBsAg, HBeAg, and HBV DNA levels over time will be tabulated by study treatment together with respective SDs. The proportion of subjects with seroclearance and seroconversion of HBsAg and HBeAg will also be tabulated by study treatment. The proportion of subjects with virologic response and the proportion of subjects with virologic or clinical relapse, defined as HBeAg, HBsAg, and/or HBV DNA levels below and above certain thresholds at different time points, respectively, will be categorized as detailed in the SAP, as applicable. Data will also be presented graphically by study phase, study treatment and by individual subject. All individual values will be presented in subject listings.

The least squares (LS) mean change from baseline in serologic parameters and HBV DNA for each study treatment and time point will be estimated with a repeated measurement model (mixed-effects model for repeated measures) including study treatment and time point as fixed effect. The model will allow for unequal variances between study treatments. A 95% confidence interval (CI) will be constructed around the difference between the LS mean of each study treatment. Other methods to evaluate the changes in serologic parameters and HBV DNA may include slope estimation, time-to-event or proportions of subjects who reach a certain level or who exceed a certain reduction.

The proportion of subjects with sustained reduction/suppression and/or sero-clearance, including but not limited to functional and partial cure, will be determined during follow-up. Single and multiple markers such as HBsAg, HBeAg, HBV DNA and ALT levels will be taken into consideration in this analysis.

Other efficacy endpoints, eg, HBV RNA and HBcrAg, will be analyzed descriptively. For continuous variables, descriptive statistics (n, mean, SD, median, minimum, maximum) will be calculated; mean difference and CIs may be calculated where appropriate and, if appropriate, a general linear mixed model will be used to compare the different study treatments. For categorical variables, frequency tables will be presented. Difference in proportions and CIs may be calculated where appropriate.

Analyses, tabulations and visualizations will be done for both treatment and follow-up phases.

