**Table 5: Time to event definitions and censored data**

Variables	Definition	Censored data
HBsAg Response	Time to a HBsAg level of $<1000$ IU/mL	Subjects who did not achieve “HBsAg $<xxx$ IU/mL” will be censored at the last HBsAg assessment
	Time to a HBsAg level $<100$ IU/mL	
	Time to a HBsAg level $<10$ IU/mL	
	Time to a HBsAg level $<0.05$ IU/mL	
HBsAg Reduction	Time to a HBsAg reduction of $> 0.3 \log_{10}$ IU/mL	Subjects who did not reduce HBsAg by “ $>xxx \log_{10}$ IU/mL” from baseline will be censored at the last HBsAg assessment
	Time to a HBsAg reduction of $> 0.5 \log_{10}$ IU/mL	
	Time to a HBsAg reduction of $> 1 \log_{10}$ IU/mL	
	Time to a HBsAg reduction of $> 2 \log_{10}$ IU/mL	
	Time to a HBsAg reduction of $> 3 \log_{10}$ IU/mL	
HBsAg Seroclearance (in all subjects)	Time to HBsAg seroclearance as defined in section 5.3.1	Subjects who did not achieve HBsAg seroclearance will be censored at the last HBsAg assessment
HBeAg Seroclearance (in HBeAg-positive subjects only)	Time to HBeAg seroclearance as defined in section 5.3.1	Subjects who did not achieve HBeAg seroclearance will be censored at the last HBeAg assessment
HBeAg Reduction	Time to a HBeAg reduction of $> 0.5 \log_{10}$ IU/mL from baseline	Subjects who did not achieve “HBeAg $<xxx$ IU/mL” from baseline will be censored at the last HBeAg assessment
	Time to a HBeAg reduction of $> 1 \log_{10}$ IU/mL from baseline	
	Time to a HBeAg reduction of $> 2 \log_{10}$ IU/mL from baseline	
HBV virological breakthrough	Time to HBV virological breakthrough as defined in section 5.3.1	Subjects who did not achieve HBV virological breakthrough will be censored at the last HBV DNA assessment during the defined time frame

HBV DNA Response	Time to a HBV DNA level <1 log10 IU/mL	Subjects who did not achieve “HBV DNA <xx log 10” will be censored at the last HBV DNA assessment
	Time to a HBV DNA level <2 log10 IU/mL	
	Time to a HBV DNA level <3 log10 IU/mL	
	Time to a HBV DNA level <100 IU/mL	Subjects who did not achieve “HBV DNA<xxxx IU/mL” will be censored at the last HBV DNA assessment
	Time to a HBV DNA level <1000 IU/mL	
	Time to a HBV DNA level <2000 IU/mL	
	Time to a HBV DNA level <20000 IU/mL	
	Time to HBV DNA < LLQ for target detected and not detected	Subjects who did not achieve HBV DNA<LLQ for both target will be censored at the last HBV DNA assessment

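### The SAP defines HBsAg/HBeAg seroclearance and seroconversion only at treatment Weeks 24 and 48, narrower than the protocol endpoint and with no rule for follow-up

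*SAP*

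**What the plan says.** Protocol 2.1 lists as a secondary endpoint the proportion of "subjects with HBsAg or HBeAg seroclearance (defined as HBsAg or HBeAg negativity, respectively, based on the assay used) during study treatment and follow-up". Seroconversion is antigen negativity together with "anti-HBs or anti-HBe antibody positivity, respectively) during study treatment and follow-up". For the extension phase the same section adds sustained sero-clearance at follow-up (FU) Weeks 12, 24 and 48, and Protocol 11.3.3 plans that "The proportion of subjects with sustained reduction/suppression and/or sero-clearance, including but not limited to functional and partial cure, will be determined during follow-up".

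SAP 5.3, Parameter Definitions, contains two consecutive entries, both labelled Seroconversion. The first describes loss of antigen only, so it is the seroclearance definition; it "is defined as a confirmed loss of HBsAg/HBeAg at week 24/48 of the treatment". The second adds appearance of the antibody and takes the selected Week 24 or Week 48 visit. Week 48 applies only to extension subjects. The status-change variable is limited to the same two visits, and under Secondary Analysis "A tabulation of the qualitative result of HBeAg and HBsAg per timepoint (week 24 and week 48) will be included".

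The closing list of Secondary Analysis covers categorical endpoints to be summarised over treatment and follow-up. It names HBsAg seroclearance and "The proportion of subjects with HBsAg seroconversion", but neither endpoint for HBeAg. Table 5 adds "Time to HBeAg seroclearance as defined in section 5.3.1" and the matching HBsAg variable, both censored at the last assessment of that antigen.

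**The concern.** A programmer who follows the derivation evaluates antigen loss at one or two treatment visits. The protocol endpoint runs through follow-up, and the schedules collect qualitative antigen and antibody results there. The list of proportions promises follow-up results, but the only definition available to it stops at the end of treatment.

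This matters because Protocol 1.4 justifies HBsAg decline as a marker by its link to subsequent HBsAg loss, and the extension explores finite treatment. Loss and seroconversion after study drug stops are the cure-related outcomes. If the rule is left open, two programmers could produce different counts from the same data.

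**Working it through.** No sample size, power or alpha depends on this point, and the plan gives no figure to reproduce. The check sets the texts side by side and counts visits.

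**Does any other SAP text supply a follow-up definition?**

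- The same section gives follow-up definitions for viral breakthrough on NA, viral relapse and biochemical relapse. It states what confirmed means for breakthrough and both relapse endpoints: two or more consecutive time points, or the last observed time point (on treatment, for breakthrough). Serology has neither a follow-up definition nor a meaning for confirmed.
- SAP 2.3 allocates visits to time points within each phase. A follow-up sample is assigned to a follow-up week, so it cannot be picked up as Week 24 or Week 48.
- Table 5 refers back to a section 5.3.1. No heading carries that number (the headings under 5.3 read 5.2.1), and the definition evidently meant is the Week 24/48 one.
- Table 4 has HBsAg level categories, including below 0.05 IU/mL. For HBeAg it has only reductions from baseline. HBeAg loss in follow-up therefore has no defined route to a proportion.

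**Which scheduled qualitative tests can the definition use?** Inputs are the protocol Time and Events Schedules. The treatment-phase row for qualitative HBsAg/HBeAg has two pre-dose marks and two later ones, read here as Weeks 24 and 48 because the table columns are broken. The SAP's own tabulation at those weeks agrees. Schedule 1 has the early withdrawal visit and FU Weeks 2, 4, 12 and 24. Schedule 2 has FU Weeks 4, 12, 24 and 48.

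| Subject | Scheduled post-baseline qualitative tests | Total | Usable at Week 24/48 |
|---|---|---|---|
| 24 weeks, Schedule 1 | Week 24 + 4 FU | 1 + 4 = 5 | 1 |
| 48 weeks, Schedule 1 | Weeks 24, 48 + 4 FU | 2 + 4 = 6 | 2 |
| 48 weeks, Schedule 2 | Weeks 24, 48 + 4 FU | 2 + 4 = 6 | 2 |
| Stops before the Week 24 window (days 155 to 182) | Early withdrawal + 4 FU | 1 + 4 = 5 | 0 |

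The last row can include Arm 1 subjects whose dosing was stopped under Amendment 4. The documents do not say how many of them stopped before Week 24.

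**Can confirmed be met?** In an extension subject, a loss at Week 24 has its next scheduled qualitative test at Week 48, which is 48 − 24 = 24 weeks later. In a 24-week subject the next test is at FU Week 2, but the SAP does not say whether a follow-up result may confirm a treatment-phase loss.

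**The case against.** The best defence is that the SAP plainly intends to cover follow-up. The list of proportions says so for HBsAg. SAP 5 analyses serology by phase and follow-up type. Table 4 counts HBsAg below 0.05 IU/mL per time point and whenever it is met at least once in a phase, and all individual values are listed. The study is exploratory, with no formal testing.

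Much of this stands, and it rules out several stronger readings that a reader might infer:

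- *Follow-up losses are never counted, or are scored 0% in every arm.* No SAP rule assigns zero, and Table 4 counts low HBsAg in follow-up. The follow-up derivation is undefined; it is not set to zero.
- *Time to seroclearance can only equal Week 24 or Week 48.* The SAP's explanation of loss refers to a negative post-baseline assessment without naming a visit, and censoring is at the last assessment with no limit to the treatment phase. The text is ambiguous.
- *Many on-treatment losses are missed.* Apart from early withdrawal, no other qualitative test appears to be scheduled on treatment. The gap is in follow-up and in early stoppers.
- *Most subjects stop by Week 24.* The documents give no such figure. Extension requires HBV DNA below 200 IU/mL by Week 20, and the suppressed subjects, 2 × 40 = 80 of the 2 × 110 = 220 targeted, enter below 60 IU/mL.

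The defence does not remove the conflict. HBsAg below 0.05 IU/mL is a quantitative threshold, whereas the protocol endpoint is negativity on the assay used. That category covers neither seroconversion nor HBeAg, and a listing is not an analysis. For HBeAg, the status-change and qualitative tables cover Weeks 24 and 48 but not follow-up.

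**Conclusion.** The point holds as a conflict between the SAP derivation, the protocol endpoint and the SAP's own list of proportions. Followed as written, the definition uses 1 of 5 or 2 of 6 scheduled qualitative tests, and none for a subject who stops before the Week 24 window. HBeAg loss and seroconversion in follow-up have no planned proportion. The HBsAg proportions in follow-up are promised without a rule.

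The counts rest on reading the broken treatment-phase schedule as Weeks 24 and 48, and on complete attendance. The number of events affected cannot be estimated from the documents. No primary result depends on this, but it should be corrected because these endpoints carry the cure-related information.

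**What to change.** In SAP 5.3 and Table 5:

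1. Define seroclearance, for HBsAg and HBeAg, as a negative qualitative result at any post-baseline qualitative visit, including early withdrawal and follow-up. Define seroconversion as that plus a positive corresponding antibody.
2. State a confirmation rule in line with the rest of the section: two or more consecutive time points, or the last observed one. Say whether a follow-up result can confirm a treatment-phase loss.
3. Date the event at the first qualifying result.
4. Report by Week 24, by Week 48 and by end of follow-up, split by the SAP's two follow-up types (NA or treatment free).
5. Add HBeAg seroclearance and seroconversion, in baseline HBeAg-positive subjects, to the list of proportions.
6. Correct the label on the first definition and the references to section 5.3.1.

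Quantitative results below the quantification limit (0.05 IU/mL for HBsAg, 0.11 IU/mL for HBeAg) may be shown as supportive only. The SAP gives these values as assay limits and nowhere equates them with qualitative negativity.

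The cost is SAP wording, derivations and some extra tables on data already scheduled. No new sampling is needed.

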#### **4.2. Exclusion Criteria**

Any potential subject who meets any of the following criteria will be excluded from participating in the study:

1. Subjects who test positive for anti-HBs antibodies.
2. Criterion modified per Amendment 3
  - 2.1. Subjects with current hepatitis A virus infection (confirmed by hepatitis A antibody IgM), HDV infection (confirmed by HDV antibody), hepatitis E virus infection (confirmed by hepatitis E antibody IgM), or HIV-1 or HIV-2 infection (confirmed by antibodies) at screening; subjects with a history of or current HCV infection (confirmed by HCV antibody). Evidence of other active infection (bacterial, viral, fungal, including acute tuberculosis) deemed clinically relevant by the investigator that would interfere with study conduct or its interpretation will also lead to exclusion.
3. Subjects with any evidence of hepatic decompensation at any time point prior to or at the time of screening:
  - a. Direct bilirubin  $>1.2x$  ULN, or
  - b. International normalized ratio (INR)  $>1.5x$  ULN, or
  - c. Serum albumin  $<$  lower limit of normal (LLN), or
  - d. Documented history or current evidence of variceal bleeding, ascites, or hepatic encephalopathy.
4. Subjects with any evidence of liver disease of non-HBV etiology. This includes but is not limited to hepatitis virus infections mentioned in exclusion criterion 2, drug- or alcohol-related liver disease, autoimmune hepatitis, hemochromatosis, Wilson's

disease, Gilbert's syndrome,  $\alpha$ -1 antitrypsin deficiency, primary biliary cirrhosis, primary sclerosing cholangitis, or any other non-HBV liver disease considered clinically significant by the investigator.

5. Subjects who have signs of HCC on an abdominal ultrasound performed within 2 months prior to screening or at the time of screening. In case of suspicious findings on conventional ultrasound the subject may still be eligible if HCC has been ruled out by a more specific imaging procedure (contrast enhanced ultrasound, CT or MRI).
6. Criterion modified per Amendment 2

6.1. Subjects with one or more of the following laboratory abnormalities at screening:

- a. Any laboratory abnormality  $>$  grade 1 (as defined by the Division of AIDS [DAIDS] Toxicity Grading Scale), with the exception of ALT/AST, considered to be clinically significant by the investigator at screening.
- b. Alpha-fetoprotein outside the normal range.

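### The SAP counts seroconversion only if the antibody was negative at baseline; the protocol endpoint has no such condition, so HBeAg seroconversion can be undercounted

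*SAP*

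**What the plan says.** **Protocol, section 2.1 (same wording in the Synopsis).** A secondary endpoint is the proportion of subjects with "seroconversion (defined as HBsAg or HBeAg negativity and anti-HBs or anti-HBe antibody positivity, respectively"), assessed during treatment and follow-up. The e-antigen part has its own population: "HBeAg (in HBeAg-positive subjects only) seroclearance and/or seroconversion". Nothing is said about the antibody at baseline.

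**SAP, section 5.3, Parameter Definitions (numbered 5.2.1 there).** Seroconversion needs confirmed antigen loss and an appearance of the antibody. On the second element: "Appearance is defined as a baseline Anti-HBs/ Anti-HBe (qualitative) with a" negative result, followed by a positive result after baseline. Then: "Both criteria should be fulfilled". The populations are in the label: "Seroconversion of HBsAg (all subjects) / HBeAg (positive subjects) at week 24 of the treatment". That label stands over two consecutive definitions. The first covers antigen loss alone and is evidently seroclearance; the second carries the antibody condition. Both name the same populations, and neither is limited to subjects who were antibody-negative at baseline.

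**Entry criteria.** Protocol section 4.2, criterion 1, excludes "Subjects who test positive for anti-HBs antibodies". Sections 4.1 and 4.2 contain no counterpart for anti-HBe.

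**The concern.** The protocol leaves the response subcategories for antigen and HBV DNA levels to the SAP, but it defines seroconversion itself. SAP section 1.1 adopts the protocol endpoints by reference. Section 5.3 then adds a condition that changes who counts, and the SAP amendment history does not mention it.

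An HBeAg-positive subject who already has anti-HBe at baseline fails the appearance test whatever happens later. If that subject loses HBeAg and is anti-HBe positive at the visit, the protocol counts a success and the SAP does not. The study report would then give a rate under the protocol's endpoint name that is not the protocol's endpoint. Planned HBeAg-positive cells are small, so a single reclassified subject is visible in an arm's rate.

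**Working it through.** The documents state no rate, power or sample size for seroconversion, so there is no planned figure to reproduce. The check is a comparison of definitions, followed by the effect of one subject.

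**1. Definitions side by side, for an HBeAg-positive subject who has lost HBeAg and is anti-HBe positive at the visit**

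| Anti-HBe at baseline | Protocol 2.1 | SAP 5.3 |
|---|---|---|
| Negative | seroconverter | seroconverter |
| Positive | seroconverter | not a seroconverter |

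If HBeAg is not lost, or anti-HBe is negative at the visit, both rules give a non-responder. The second row is the only place where the baseline condition matters. For HBsAg that row should be empty, because of exclusion criterion 1.

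**2. Planned HBeAg-positive cells.** Inputs are the arm sizes in protocol section 3.1 and the planned HBeAg-positive shares of 40% (currently not treated) and 30% (virologically suppressed).

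- Not treated: 30 × 0.40 = 12 per active arm; 10 × 0.40 = 4 on placebo+NA.
- Suppressed: 30 × 0.30 = 9 on active+NA; 10 × 0.30 = 3 on placebo+NA.

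These match the 4/12 and 3/9 in protocol Table 7.

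**3. Effect per subject.** Let n be the HBeAg-positive subjects in the cell, s those who seroconvert under both rules, and u those in the second row of the table. With the denominator left at n:

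- protocol rate = (s + u)/n
- SAP rate = s/n
- shortfall = u/n

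For u = 1, the shortfall is 1/12 = 8.3 points, 1/9 = 11.1 points, 1/4 = 25 points or 1/3 = 33.3 points.

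**4. Illustration with assumed counts.** In a cell of 12, suppose 3 subjects meet the protocol definition and 1 of them was anti-HBe positive at baseline. The protocol rate is 3/12 = 25.0%. The SAP rate is 2/12 = 16.7%. Taking that subject out of the denominator as well gives 2/11 = 18.2%.

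**5. What cannot be computed.** The expected total undercount is N × f × r. N is the number of HBeAg-positive subjects, f the share with anti-HBe at baseline, and r the chance that such a subject meets the protocol definition. N is planned at 2 × (0.40 × 70 + 0.30 × 40) = 2 × 40 = 80. The documents give neither f nor r. With f assumed at 5% to 20%, N × f is 4 to 16 subjects who cannot count under the SAP. The undercount among them runs from zero, if none meets the protocol definition, to all of them, if every one does.

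**The case against.** **The size.** A reader might take 4 to 16 as the number of responders lost. The documents do not support that. It is the number who could not qualify under an assumed baseline share, and it leaves out whether they lose HBeAg. The only on-drug evidence in the protocol (section 1.1, 28 days of dosing) is that HBeAg did not change notably. This objection stands.

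**The denominator.** A reader might take it as stated that these subjects remain in the denominator. It is not stated. It follows from the population label and the ITT set used for efficacy. The SAP's list of secondary proportions names HBsAg seroconversion, which is unaffected, and omits HBeAg seroconversion, although protocol section 11.3.3 asks for both to be tabulated. The inference is still reasonable. Where the SAP wants an at-risk population it says so: ALT normalization needs ALT above ULN at baseline, and viral relapse needs HBV DNA below 20 IU/mL at end of treatment.

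**Missing baseline antibody.** One might add that a missing baseline result also blocks counting. This has little force. Anti-HBe is scheduled at screening and on Day 1, and baseline is the last value before the first dose, so both would have to be missing.

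**The SAP rule is a coherent reading.** Seroconversion can mean a newly appearing antibody, and protocol section 11 leaves specific details to the SAP. That would justify the stricter numerator only with a denominator of subjects antibody-negative at baseline, and with the departure recorded. Neither is present.

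**The information is kept elsewhere.** Baseline anti-HBe and status changes at Weeks 24 and 48 are tabulated, and all values are listed. Borderline anti-HBe counts as negative, so those subjects can still qualify. This limits the harm. However, the status changes are shown marker by marker, so the joint pattern would have to be rebuilt from the listings.

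**Conclusion.** The point holds for HBeAg seroconversion. The SAP applies a baseline antibody condition that the protocol endpoint lacks, and it scores some protocol-defined seroconverters as non-responders. That mismatch rests on the text alone and needs no assumption.

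The error can only lower the HBeAg rate. It equals the number of subjects who were anti-HBe positive at baseline and meet the protocol definition, divided by the cell size: 8 points per subject in a cell of 12 and 11 in a cell of 9. This takes the planned cell sizes and the inferred denominator. How many such subjects there will be is unknown and may be none.

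The importance is minor. This is a secondary endpoint in an exploratory study without formal hypothesis testing. The point concerns the antibody condition only, not the visits at which seroconversion is assessed.

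**What to change.** In SAP section 5.3, derive seroconversion as in protocol section 2.1: antigen loss and antibody positive at the time point, whatever the baseline antibody. If appearance of new antibody is also of interest, report it as a separate, separately named measure, with only subjects antibody-negative at baseline in the denominator. In either case, write one sentence stating the denominator.

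The cost is that wording and one condition in the derivation program. No new data are needed and nothing changes for subjects.
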